1.10 Timetable/Schedule of Events

All study procedures will be performed according to the scheduled outlined in the Study Flow Table

2.2 Research Staff Training

We will provide training to all clinical research staff prior to any contact with study participants including:

- Overview of protocol and study organization
- Consent process
- Completion of study questionnaires
- Use of study ancillary supplies (Zio AT ECG, thermometer, pulse oximeter, home specimen collection and shipping)
- Use of REDCap

For those research staff collecting specimens or otherwise exposed to potentially infectious individuals, we will provide training for:

- Sample collection and handling of sample collection kits;
- Sample collection and processing activities;
- Use of personal protective equipment (PPE).

2.3 Resources Available

Nitazoxanide, Ribavirin, Hydroxychloroquine sulfate and corresponding placebo tablets will be provided at no charge to the study participants. The study required devices (Zio AT monitoring device, pulse oximeter, thermometer) as well as at home specimen collection materials and associated shipping materials will also be provided without expense to the study participants.

Staffing and coordination of the study will be run through clinical coordinating staff lead by [name] with supplemented by our CTSA hub (NJ Alliance for Clinical and Translational Science [NJ ACTS]) directed by PI [name]. [name] team has led large international trials including over 100 sites funded by NIH. NJ ACTS runs the 5 CRUs in which most study visits will occur and a highly experienced team of has 22 clinical research coordinators who can be deployed for this work. These coordinators are facile in the use of iPad-based electronic consents (eConsents) and clinical report forms (eCRFs). Additional coordinators will be recruited from the University employees.

The biospecimen management and storage of CBC and chemistry blood samples will occur at Robert Wood Johnson University Hospital. Blood specimen for SARS-CoV-2 antibody testing will be packaged and shipped to RUCDR (who will provide the collection kits), where it will be processed, frozen and stored prior to transport to the [name] Lab for analysis.

The nasal swab specimens testing will occur at The Translational Genomics Research Institute (TGen), an affiliate of City of Hope. TGen will provide Sample collection kits and Viral Load Testing in support of the primary endpoint for this study.

3.0 Multi-Center Research N/A

4.0 Participant Considerations

4.1 Participant Selection and Enrollment Considerations

A. Method to Identify Potential Participants

The study population will consist of those with a known positive test for SARS-CoV-2 who have no or mild symptoms of infection. We anticipate these individuals will be identified due to their participation in ongoing (and upcoming) screening programs (e.g., the RCC study, hospital wide screenings, first responder screenings). We will develop relationships with these screening programs and, if agreeable, the programs will have participants self-identify as interested in volunteering for future research. We will reach out directly to potentially eligible participants identified in this manner. We will determine if they are asymptomatic or mildly symptomatic and, if eligible, offer participation in the trial. We will also recruit participants from the general public through advertisements in local press, letters to local clinicians, and emails to university staff and faculty. Interested participants will review the trial methods and complete the eligibility questionnaire. We will also send an email to employees of Robert Wood Johnson University Hospital, University Hospital, and Rutgers University seeking volunteers with SARS-CoV-2-positive tests within the past 7 days.

B. Recruitment Details

We will recruit eligible participants from the RCC study or participants identified from the community who test positive for SARS-CoV-2. The recruiting materials will direct the potential participants to online materials that include information about the trial, consent forms, and a screening questionnaire to assess eligibility.

C. Participant Screening

We will require all volunteers to complete an on-line screening questionnaire which will identify eligible participants. Based on the responses to the screening questionnaire, the volunteers will be notified if they could be eligible for the study. Eligible participants will be asked to provide their name, e-mail address, and phone number so that study staff may follow up with them to further assess their willingness to participate in the trial.

The participant will then come to the study location at [name] to complete final screening for the trial eligibility. P02 will be measured and 6 lead portable electrocardiogram will be performed; if PO2<92% or QT interval is QTc interval > 450 mSEC the participant will be excluded. Females of childbearing potential will have a urine test to confirm that they are not pregnant.

Inclusion Criteria

- 1. Documented SARS-CoV-2 infection by qPCR assay without symptoms or with mild symptoms consistent with COVID-19 performed within the past 7 days
- 2. Age ≥21

Exclusion Criteria

- 1. COVID-19 symptoms requiring hospitalization
- 2. PO2 < 92%
- 3. Short of breath at time of enrollment
- 4. Retinal eye disease
- 5. Known glucose-6 phosphate dehydrogenase (G-6-PD) deficiency
- 6. Known chronic kidney disease, stage 5 or receiving dialysis
- 7. Current use of:
 - Class 3 AAD (amiodarone, dronaderone, dofetilide, sotalol)
 - Class 1A AAD (procainamide, quinidine, disopyramide)
 - Flecainide
 - SSRI: citalopram (Celexa), Escitalopram (Lexapro)
 - chlorpromazine
 - Cilostazol (Pletal)
 - Donepezil (Aricept)
 - Droperidol
 - Fluoconazole
 - Methadone
 - Ondansetron (Zofran)
 - Thioridazine
 - Macrolides (clarithromycin, erythromycin)
 - Fluroquinolones (ciprofloxacin, levofloxacin, moxifloxacin)
 - Tamoxifen citrate
- 8. Pregnancy or women who are breast feeding
- 9. Inability to tolerate oral medications
- 10. Allergy or prior adverse reaction to either hydroxychloroquine sulfate, ribavirin, or nitazoxanide
- 11. Allergy to adhesives
- 12. QTc interval > 450 mSEC for men and women
- 13. History of Torsade de Pointes VT or prior cardiac arrest or congenital long QT interval
- 14. Non-English-speaking

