Following a 200 mg oral dose, hydroxychloroquine reached a Cmax of 129.6ng/mL with a Tmax of 3.26h in the blood and a Cmax of 50.3ng/mL with a Tmax of 3.74h in the plasma. Oral hydroxychloroquine has an absorption half-life of 3-4 hours. A 200 mg oral dose of hydroxychloroquine has a half-life of 537 hours or 22.4 days in blood, and 2963 hours or 123.5 days in plasma. Steady state modelling of steady state dosing of HCQ has been carried out, showing that a 400 mg BID loading dose, followed by 200 mg BID for 5 days results in the unbound Css of 600 ng/ml, with lung concentrations >10,000 ng/ml¹¹(Smith et al 2020, data on file). Based on a clinical study, hydroxychloroquine is a weak-to-moderate inhibitor of CYP2D6 (causing about a 65% increase in exposure of metoprolol).

After oral ingestion of ribavirin, the plasma concentration exhibits a characteristic three-phase profile, consisting of two rapid phases (absorption and distribution) and one long terminal elimination phase. Ribavirin is promptly absorbed into circulation, with the help of gastrointestinal, sodium-dependent nucleoside transporters in the proximal small bowel. The average time to reach Cmax is 2 hours after oral administration of 1200 mg ribavirin. Following administration of 1200 mg/day with food for 12 weeks mean±SD (n=39; body weight greater than 75 kg) AUC was 25,361±7110 ng·hr/mL and C was 2748±818 ng/mL. The terminal half-life of ribavirin following administration of a single oral dose of ribavirin is about 120 to 170 hours. The total apparent clearance following administration of a single oral dose of ribavirin is about 26 L/h. After 5 days of dosing, Ribavirin levels approaching 3000 ng/ml are achieved with 600 mg BID dosing (Wu, et al, 2018). Ribavirin is eliminated by metabolism and renal elimination, with the latter accounting for about 5–15% of single dose elimination.

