1.3 Research Design and Methods

We will conduct a randomized clinical trial enrolling eligible participants who are determined to be SARS-CoV-2-positive (e.g., via Rutgers Corona Cohort [RCC] study, hospital or other screening programs) who volunteer for the study. Specifically, we will enroll 70 participants whose test has been performed within the past 7 days who are either asymptomatic or mildly symptomatic at baseline. Mild COVID-19 symptoms include new cough, sore throat, fever, myalgias, new vomiting or diarrheaor change in smell or taste. Illness requiring hospitalization, or those who present with hypoxia (PO2<92%) or shortness of breath at time of enrollment will be classified as significantly symptomatic and excluded from study participation. People who are allergic or intolerant to NTZ, RBV or HCQ will be excluded. We will randomly allocate participants stratified by presence of mild symptoms to 1) NTZ, RBV and HCQ or 2) placebo. Treatment with the investigational agents or placebo will continue for 5 days. Viral load will be assessed at baseline (day 0) as well as at days 3, 6, and 10 to monitor response to antiviral treatment. Immune status will be determined by antibody testing of blood collected at baseline and day 28.

Prior to initiating enrollment, we will prepare two randomization tables for treatment assignment using permuted blocks of six which will be provided to the research pharmacist. One table will be used for participants without symptoms and the other will be used for those with mild symptoms. The pharmacist will prepare kits containing the 5-day supply of study medications (investigational drugs/placebo) which will be sequentially numbered in accordance with the randomization tables. The contents of each kit (investigation drugs/placebo) will be indistinguishable. Study staff will establish symptom status at the baseline visit, and per pharmacy order, provide the participant the next numbered medication kit in the participant's stratum (no symptoms/mild symptoms). The study investigators, staff interacting with the participants are all masked to treatment assignment

A. Research Procedures

- 1. Study Procedures:
 - Day 0/1 Screening/Baseline Visit (in person)
 - Pre-screen via online screening form to confirm eligibility
 - Obtain informed consent for trial enrollment
 - Medical history
 - Medication history
 - Document symptoms (if any)

- o Take temperature, PO2, Pulse
- Q-T interval assessment

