 - Arm 1: NTZ 1000 mg (2 x 250 mg tablets BID for day one) and then 1000 mg (2 x 250 mg tablets BID for 4 days) RBV 1200 mg (3 x 200 mg capsules BID day one) and then RBV 800 mg (2 x 200mg capsules BID for 4 days) HCQ 800 mg (2 x 200 mg tablets bid day one) and then HCQ 400 mg (1 x 200 mg tablet BID for 4 days)
 - Arm 2: Placebo for NTZ (2 tablets BID for day one and then 2 tablets BID for 4 days) Placebo for RBV (3 capsules BID day one and then 2 capsules BID for 4 days) Placebo for HCQ (2 tablets bid day one and then 1 tablet BID for 4 days)

Hydroxychloroquine sulfate (HCQ)

One hydroxychloroquine sulfate tablet contains 200 mg of hydroxychloroquine sulfate, which is the equivalent to 155 mg base.

Ribavirin (RBV)

One ribavirin capsule contains 200 mg of ribavirin.

Nitazoxanide (NTZ)

One nitazoxanide tablet contains 500 mg of nitazoxanide.

Take all tablets/capsules with a meal or a glass of milk.

All study drugs should be stored at room temperature 20°-25° (68°-77 °F).

Concomitant Medications & Supportive Guidelines

Study participants can receive full supportive care therapies concomitantly during the study. We will advise rest, fluids, hot/ showers/baths. We will recommend NO antipyretics since they make infections worse by interfering with the generation of fever--which is considered beneficial until it reaches 102 degrees F.

B. Participant Enrollment

We will identify asymptomatic or mildly symptomatic participants who test positive for SARS-CoV-2 from the Rutgers Coronavirus Cohort (RCC) and hospital screening programs, or from the community through advertisements at our medical center, university, and in local publications. The recruiting materials will direct the potential participants to online materials that include information about the trial, consent forms, and a screener questionnaire to assess eligibility. If eligible for the trial, we will answer any questions and provide as much time as needed to review all study materials. The participant may then electronically sign the consent or, as an alternative, wait until the initial visit to re-review and sign the consent. The consenting process will be primarily performed remotely to protect research personnel.

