1.6 Study Variables

A. Primary Outcome:

Viral load at 10 days post randomization

B. Other measures

Age, Gender Race/ethnicity BMI Co-morbidity:

- Diabetes mellitus
- Hypertension
- Chronic bronchitis, emphysema, or chronic obstructive pulmonary disease (COPD)
- Other lung disease
- Coronary artery disease, peripheral artery disease, angina, or heart attack (myocardial infarction)
- Congestive heart failure
- Stroke or transient ischemic attack (TIA)
- Atrial fibrillation
- Cancer other than non-melanoma skin cancer
- Chronic kidney disease (CKD)
- Crohn's disease, ulcerative colitis, or inflammatory bowel disease (IBD)
- Rheumatoid arthritis (RA), psoriasis, systemic lupus, multiple sclerosis, or another autoimmune disorder
- Allergic rhinitis

Medications Symptoms Household infection (confirmed or suspected)

List variables of interest

Treatment Variables:

- Treatment Compliance
- Adverse Events (number/percentage/grade)

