1.7 Drugs/Devices/Biologics

Generic name: Hydroxychloroquine sulfate

[figure not shown]
Commercial name: Plaquenil

For complete information please refer to the package inserts at http://dailymed.nlm.nih.gov/dailymed/Hydroxychloroquine

Chemical name: 7-Chloro-4-[4-[ethyl-(2-hydroxyethyl) amino]-1-methylbutylamino] quinolone

Source: Commercially available

C18H26CIN3O•H2SO4

Molecular Weight: 433.95

Hydroxychloroquine sulfate tablets, USP contain 200 mg hydroxychloroquine sulfate, equivalent to 155 mg base, and are for oral administration.

Pharmacokinetics: Following a single 200 mg oral dose of hydroxychloroquine sulfate to healthy males, the mean peak blood concentration of hydroxychloroquine was 129.6 ng/mL, reached in 3.26 hours with a half-life of 537 hours (22.4 days). In the same study, the plasma peak concentration was 50.3 ng/mL reached in 3.74 hours with a half-life of 2963 hours (123.5 days). Urine hydroxychloroquine levels were still detectable after 3 months with approximately 10% of the dose excreted as the parent drug. Results following a single dose of a 200 mg tablet versus I.V. infusion (155 mg), demonstrated a half-life of about 40 days and a large volume of distribution.

Mechanism of Action: The precise mechanism by which hydroxychloroquine exhibits activity against *Plasmodium* is not known. Hydroxychloroquine, like chloroquine, is a weak base and may exert its effect by concentrating in the acid vesicles of the parasite and by inhibiting polymerization of heme. It can also inhibit certain enzymes by its interaction with DNA.

Warnings:

Ocular: Irreversible retinal damage has been observed in some patients who had received hydroxychloroquine sulfate. Significant risk factors for retinal damage include daily doses of hydroxychloroquine sulfate greater than 6.5 mg/kg (5 mg/kg base) of actual body weight, durations of use greater than five years, subnormal glomerular filtration, use of some concomitant drug products such as tamoxifen citrate and concurrent macular disease.

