Cardiac Effects, including Cardiomyopathy and QT prolongation: Post-marketing cases of life-threatening and fatal cardiomyopathy have been reported with use of hydroxychloroquine sulfate as well as with use of chloroquine. Hydroxychloroquine sulfate prolongs the QT interval. Ventricular arrhythmias and torsades de pointes have been reported in patients taking hydroxychloroquine sulfate (see OVERDOSAGE). Therefore, hydroxychloroquine sulfate should not be administered with other drugs that have the potential to prolong the QT interval.

Worsening of psoriasis and porphyria

Proximal Myopathy and Neuropathy

Neuropsychiatric events, including suicidality

Hypoglycemia: Hydroxychloroquine sulfate has been shown to cause severe hypoglycemia including loss of consciousness that could be life threatening in patients treated with or without antidiabetic medications

General precautions: General: Use with caution in patients with gastrointestinal, neurological, or blood disorders, and in those with a sensitivity to quinine.

Hepatic/Renal Disease: Antimalarial compounds should be used with caution in patients with hepatic disease or alcoholism or in conjunction with known hepatotoxic drugs. A reduction in dosage may be necessary in patients with hepatic or renal disease, as well as in those taking medicines known to affect these organs.

Hematologic Effects/Laboratory Tests: Antimalarial compounds should be used with caution in patients with hepatic disease or alcoholism or in conjunction with known hepatotoxic drugs. Periodic blood cell counts should be performed if patients are given prolonged therapy.

Hydroxychloroquine sulfate should be administered with caution in patients having glucose-6-phosphate dehydrogenase (G-6-PD) deficiency.

Dermatologic Effects: Dermatologic reactions to hydroxychloroquine sulfate may occur and, therefore, proper care should be exercised when it is administered to any patient receiving a drug with a significant tendency to produce dermatitis.

Drug Interactions (include but not limited to): Digoxin, Insulin or antidiabetic drugs, Drugs that prolong QT interval and other arrhythmogenic drugs, Mefloquine and other drugs known to lower the convulsive threshold, Antiepileptics, Methotrexate, Cyclosporin, Praziquantel, Antacids and kaolin, Cimetidine, Ampicillin.

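### The eligibility and concomitant-medication rules do not exclude current or recent use of the study drugs, so a hydroxychloroquine user can be randomised to either arm.

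*Combined protocol and SAP*

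**What the plan says.** **Eligibility.** The exclusion criteria in Section 4.1 C name the study drugs once, in criterion 10: "Allergy or prior adverse reaction to either hydroxychloroquine sulfate, ribavirin, or nitazoxanide". Section 1.3 gives the same rule in other words: "People who are allergic or intolerant to NTZ, RBV or HCQ will be excluded". Criterion 7 lists barred current medications, from antiarrhythmics to tamoxifen. Hydroxychloroquine, chloroquine, ribavirin and nitazoxanide are not among them, and no washout is stated.

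**During the trial.** The concomitant-medication text in Section 1.3 A reads "Study participants can receive full supportive care therapies concomitantly during the study" and advises only against antipyretics.

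**Who might be taking the drug.** Section 1.6 B includes, among comorbidities to record, "Rheumatoid arthritis (RA), psoriasis, systemic lupus, multiple sclerosis, or another autoimmune disorder". Section 1.2, in its summary of sudden-death reports, mentions rheumatoid arthritis and lupus as conditions for which hydroxychloroquine had been given.

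**Persistence.** Section 1.2 states "A 200 mg oral dose of hydroxychloroquine has a half-life of 537 hours or 22.4 days in blood" and gives 123.5 days in plasma. Section 1.7 repeats both and adds a figure of about 40 days.

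**Analysis.** Section 6.1 analyses participants in their randomised groups, with treatment, time and their interaction as predictors. Medication history and concomitant medications are collected (Section 1.3 A and D), but no eligibility or analysis rule uses them.

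**The concern.** The primary objective compares the three-drug combination with placebo on the slope of viral load. That contrast means what it says only if placebo participants are free of the study drugs. As written, the criteria admit someone on maintenance hydroxychloroquine, or someone given it for COVID-19 in the up to 7 days between the qualifying test and entry.

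Three things follow:

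- **Placebo arm.** The user counts as untreated. If hydroxychloroquine contributes to the regimen's effect, the slope difference is pulled toward zero.
- **Arm 1.** The user receives study hydroxychloroquine in addition to their own. No section addresses this.
- **QT endpoint.** For a maintenance user, the baseline reading already contains any drug effect, so change from baseline is measured from the wrong starting point in either arm.

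A related inconsistency concerns azithromycin. The macrolide entry in criterion 7 names clarithromycin and erythromycin. Section 1.2 reports a discontinuation for QT prolongation on hydroxychloroquine plus azithromycin, and Section 1.7 states that "hydroxychloroquine sulfate should not be administered with other drugs that have the potential to prolong the QT interval". A reader cannot tell whether azithromycin is covered.

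**Working it through.** **1. The plan's own power.** Inputs from Section 1.5: slope difference 0.2 log10 per day, between-person slope SD 0.2, within-person SD 0.5 or 1, measurements on days 0, 3, 6 and 10, 30 per group in the power table, 35 per arm planned. No significance level is stated; two-sided 5% is assumed.

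The mean day is 19/4 = 4.75, and the sum of squared deviations is 22.5625 + 3.0625 + 1.5625 + 27.5625 = 54.75. With complete data, the interaction test is close to a two-sample test on per-person slopes, whose SD is √(0.2² + SD²/54.75).

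- SD 0.5: slope SD = √(0.04 + 0.0046) = 0.211. Power at 30 per arm is 95.0% (plan: 94% and 94%).
- SD 1: slope SD = √(0.04 + 0.0183) = 0.241. Power at 30 per arm is 88.4% (plan: 87% and 84%).

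The 84% cell is 4.4 points below this check. The plan's conclusion of more than 80% power reproduces on its own assumptions, which include no floor at the assay's quantification limit.

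**2. Dilution of the contrast.** Let k of 35 placebo participants be users who receive a share c of the full effect. The contrast shrinks by c × k/35. Both k and c are assumptions.

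| | k = 2 | k = 4 |
|---|---|---|
| c = 1/3 | 1.9% | 3.8% |
| c = 1 | 5.7% | 11.4% |

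**3. Effect on power.** With f = k/35, the detectable difference becomes 0.2 × (1 − f × c). At SD 1, the less favourable case:

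| f | c | 30 per arm | 35 per arm |
|---|---|---|---|
| 0 | – | 88.4% | 92.7% |
| 5% | 1/3 | 87.3% | 91.9% |
| 5% | 1 | 85.0% | 90.1% |
| 10% | 1 | 81.1% | 86.8% |
| 20% | 1 | 71.4% | 78.0% |

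Power falls below 80% when f × c reaches about 0.11 at 30 per arm or 0.18 at 35. Simulation gives slightly lower values, because mixing users with non-users also widens the placebo slopes. In the 10% row it gives 79.0% and 86.2%. The worst corner of the assumed range (0.114) is thus at or just below 80% power with 30 per arm, and above it with 35.

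**4. Recent past use.** The fraction remaining after d days is 2^(−d/half-life). With 22.4 days, 2^(−7/22.4) = 0.81 and 2^(−28/22.4) = 0.42. With 123.5 days in plasma the fractions are 0.96 and 0.85. These apply a single-dose half-life as simple exponential decay and are approximate.

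**5. Does persistence mean activity?** Section 1.2 gives an effective in vitro range of 0.24 to 2.4 µg/ml. The cited blood peak after one 200 mg dose is 129.6 ng/mL, or 0.13 µg/ml, which is below that range. The modelled steady-state level of 600 ng/ml lies inside it, but refers to a loading regimen during treatment. Neither figure describes residual levels after stopping.

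**The case against.** The strongest case on the other side is that the consequence is small and unproven. No user count is given. Hydroxychloroquine is one of three components, each described in Section 1.2 as having modest effects, so c = 1 is extreme. With 5% users and c = 1/3, power falls by 1.1 points (88.4% to 87.3%). Any bias in the primary test is toward no difference, which is conservative for a superiority claim. The retinal-disease and QTc exclusions remove some users, medication history would identify others, and the screening questionnaire, which is not in the documents, may ask. All of this stands and limits the size of the point. It does not close the gap, because no written criterion tells staff to turn such a person away.

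Four stronger readings are tempting, and the documents do not support them:

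- *That the trial expects hydroxychloroquine users.* Section 1.6 is a list of variables to record and predicts nothing about enrolment. Section 1.2 mentions rheumatoid arthritis and lupus in one case report each. Users are possible, no more.
- *That maintenance users add drug-related QT change and side effects to placebo.* Their QT effect is already in the baseline reading, and an adverse event must be new or worsening and at least grade 3 to be recorded.
- *That the Section 1.7 warning covers doubled hydroxychloroquine.* It concerns other QT-prolonging drugs.
- *That a long half-life makes past users actively treated controls.* Residual antiviral activity is not shown.

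On azithromycin, the macrolide entry can be read as a whole class with two examples. That reading is possible, which is why the text needs reconciling.

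**Conclusion.** The omission is certain: nothing in the visible criteria or concomitant-medication text excludes current or recent use of the study drugs, and the analysis has no provision for it. Followed as written, the rule permits contaminated controls in one arm and unaddressed double exposure in the other.

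The size is uncertain and probably modest: roughly 2% to 11% shrinkage of the slope contrast under assumed values of 2 to 4 users among 35 and a one-third to full share of effect. At the planned 35 per arm, that range alone would not take power below 80% on the plan's own assumptions. The point is strongest for current use. For recent past use it is a reasonable precaution, since persistence of drug is documented in the protocol but persistence of effect is not. It should be corrected, but it does not by itself threaten the trial's conclusion.

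**What to change.** 1. Add current use of hydroxychloroquine, chloroquine, ribavirin or nitazoxanide to exclusion 7, and align the sentence in Section 1.3.
2. Add a look-back for recent use. The sponsor should set and justify it: the cited half-lives (22.4, about 40 and 123.5 days) could imply very different windows, so the reasoning needs to be written down.
3. Add one question to the online screener and check it against the medication history already taken at baseline.
4. State in the concomitant-medication text that open-label use of these drugs during days 0 to 10 is recorded as a protocol deviation. Keep the intention-to-treat analysis and report the number of such participants by arm.
5. Reconcile the macrolide entry in exclusion 7 with Sections 1.2 and 1.7, so that it is clear whether azithromycin is covered.

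The cost is a few lines of text and one screener question. The downside is some volunteers screened out. That should be few for current use; for recent use it depends on how long a look-back the sponsor chooses.
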